3.1. Description of Major Components

3.1.1. OCS Heart Console

The OCS Heart Console is the reusable, non-sterile portable enclosure incorporating the electronics, software, fluid pumping systems, monitoring systems, power supply, batteries, gas cylinder, mobile base and Wireless Monitor. The Wireless Monitor displays information and allows the user to adjust certain settings.

The OCS Heart Console provides a rigid compartment to house and securely connect to the HPM during transport. The OCS Heart Console connects to a mobile base with locking wheels.

3.1.2. Heart Perfusion Set (HPS)

The Heart Perfusion Set (HPS) consists of the Heart Perfusion Module (HPM) and Disposable Accessories. The HPM provides a closed circulatory system to protect, maintain and support the heart. It uses a physical conduit to connect to the heart, incorporates various sensors, and interfaces with the OCS Heart Console to oxygenate, warm and circulate the perfusate.

The accessories are intended to:

- Collect and process the donor blood
- Prime and then infuse the OCS Heart Solution to the HPM
- Connect the heart to the HPM circuit
- Facilitate monitoring of the heart operation
- Infuse cardioplegia to terminate the preservation.

The HPM provides the sterile blood circuit and protected environment for a heart within the OCS. It is designed as a single-use, pre-assembled module that mounts into the OCS. The heart is instrumented

within the heart chamber of the HPM. The Wireless Monitor displays measurements made within the HPM. The HPM includes:

- Dual lid heart-specific heart chamber
- Integrated and easily accessible blood sampling and de-airing manifold
- Integrated pulsatile pump head interface
- Integrated low shear titanium blood warmer
- Integrated blood oxygenator (or gas exchanger)
- Integrated sensors (pressure and temperature) and circuitry to communicate with the Console.

[figure not shown]
3.1.3. OCS Heart Solution Set

The OCS Heart Solution Set consists of two proprietary heart preservation solutions, a Priming Solution and a Maintenance Solution, to replenish the nutrients and hormones (adenosine) that the metabolically active donor heart requires. The solutions are packaged in a three-chamber bag (nominal volume of 500 ml per chamber). At the time of use, the Priming Solution (500 ml) is dispensed into the HPM. The Maintenance Solution is manufactured as two component solutions (500 ml each) that are individually manufactured and then mixed immediately before infusion into the HPM. Additives are required at the time of use. The additives are not supplied by TransMedics, and are added by user.

The OCS Heart Solution Set is not intended to be administered directly to the donor or the recipient. The donor heart is arrested prior to removal using a standard cardioplegia solution. Prior to transplantation into the recipient, the donor heart is arrested on the OCS through the use of a standard cardioplegia solution, at which time the perfusate (including the donor blood, Priming Solution and Maintenance Solution) are flushed from the donor heart.

3.1.4. Mode of Action - Overview

The OCS Heart System preserves the heart in a near-physiological, beating state by perfusing the heart with a warmed, donor-blood based perfusate that is supplemented with nutrients and oxygen in a controlled and protected environment referred to as the circuit. The circuit is illustrated in [Figure 9](#) below. The OCS contains a pulsatile pump that directs flow through the gas exchanger, to be oxygenated, and then through the blood warmer and then to the aorta of the donor heart. An additional perfusate component, known as the TransMedics Maintenance Solution, is infused into this circuit. The heart consumes oxygen and nutrients as the blood travels from the aorta through the coronary arteries and returns blood to the circuit through its pulmonary artery. The OCS maintains the blood at a constant temperature, oxygenates the perfusate at a constant rate, and provides perfusate in a pulsatile flow at a constant rate.

Figure 9: Schematic of the OCS Heart System Fluid Flow

4. TRIAL OBJECTIVES

The objective of Heart EXPAND CAP is to provide additional data evaluating the safety and effectiveness of the OCS Heart System to preserve and assess donor hearts that do not meet current standard donor heart acceptance criteria for transplantation to potentially improve donor heart utilization for transplantation at a range of transplant centers in the U.S. and to permit patients and physicians access to the OCS Heart System while a PMA application is under preparation and review.

The donor hearts to be evaluated in this trial do not meet current standard donor heart acceptance criteria for one or more of the following reasons:

- Expected total cross-clamp time of ≥ 4 hours
- Expected total cross-clamp time of ≥ 2 hours PLUS one or more of the following risk factors:
 - Donor age 45-55 years inclusive, with no coronary catheterization data; or
 - Donor age ≥ 55 years; or

- Left ventricular septal or posterior wall thickness of >12 mm, but ≤16 mm; or
- Reported down time of ≥ 20 min, with stable hemodynamics at time of final assessment; or
- Left heart ejection fraction (EF) ≥40%, but ≤50% at time of acceptance of offer; or
- Donor angiogram with luminal irregularities with no significant CAD (≤50%); or
- History of carbon monoxide poisoning with good cardiac function at time of donor assessment; or
- Social history of alcoholism with good cardiac function at time of donor assessment; or
- History of diabetes without significant CAD (≤50%) on angiogram.

4.1. Type of Trial

The Heart EXPAND CAP is a prospective, single-arm continuation protocol. The CAP seeks to provide additional data on the safety and effectiveness of the OCS™ Heart System for donor hearts that today may not be transplanted due to the limitations associated with cold storage technique due to the impact of ischemia injury. The CAP permits patients and physicians access to the OCS Heart System while a PMA application is under preparation and review.

4.2. Trial Size and Subject Follow-up

This trial will be conducted at up to 8 institutions, in the United States and will include 75 transplanted heart recipients. The number of subjects was determined based on the enrollment rate for Heart EXPAND and following FDA guidelines for CAPs.

Subjects will be followed for 12 months from the date of transplantation (some of which will be post-market). The summary of follow-up assessments are is summarized in [Appendix 2](#):

- All subjects will be followed from transplant to discharge.
- Patient and graft survival will be documented at Day-30 post transplant.
- Subjects will be followed at 6 and 12 months post-transplant as summarized in Appendix 2.

5. TRIAL ENDPOINTS

5.1. Primary Endpoint

A composite of patient survival at Day 30 and absence of severe primary heart graft dysfunction (PGD) (LV or RV) in the first 24 hours post-transplantation according to ISHLT consensus manuscript (as defined in [Appendix 1](#)).

5.2. Secondary Endpoints

- Patient survival and graft survival at Day-30 post transplantation

- Incidence of severe primary heart graft dysfunction (PGD) (LV or RV) in the first 24 hours post-transplantation according to ISHLT consensus manuscript (as defined in [Appendix 1](#))
- Rate of donor heart utilization, defined as the proportion of eligible donor hearts that were successfully transplanted after preservation and assessment on the OCS Heart System.

5.3. Safety

The safety endpoint is defined as the incidence of heart graft-related Serious Adverse Events (HGRSAEs) in the first 30 days post heart transplantation, defined as:

- Moderate or Severe primary heart graft dysfunction (PGD) (left or right ventricle) (not including rejection or cardiac tamponade) according to ISHLT consensus manuscript.
- Primary graft failure requiring re-transplantation.

5.4. Other Endpoints

- Patient survival at 6 and 12 months post-transplant
- Incidence of primary graft failure requiring re-transplantation through 12 months post-transplant
- Duration of initial post-transplant ICU stay
- Duration of initial post-transplant hospital stay.

6. TRIAL POPULATION

The trial will consist of 75 heart transplant recipients, aged >18 years, at up to 8 investigational sites in the US.

6.1. Donor Eligibility Criteria

Donor Inclusion Criteria

Donor hearts are required to meet at least one of the following inclusion criteria:

- Expected total cross-clamp time of ≥ 4 hours; or
- Expected total cross-clamp time of ≥ 2 hours **PLUS** one of the following risk factors:
 - Donor age 45-55 years, inclusive, with no coronary catheterization data; or
 - Donor age ≥ 55 years; or
 - Left ventricular septal or posterior wall thickness of >12 mm, but ≤ 16 mm; or
 - Reported down time of ≥ 20 min, with stable hemodynamics at time of final assessment; or
 - Left heart ejection fraction (EF) $\geq 40\%$, but $\leq 50\%$ at time of acceptance of offer; or
 - Donor angiogram with luminal irregularities with no significant CAD ($\leq 50\%$); or

- History of carbon monoxide poisoning with good cardiac function at time of donor assessment; or
- Social history of alcoholism with good cardiac function at time of donor assessment; or
- History of diabetes without significant CAD on angiogram ($\leq 50\%$).

Donor Exclusion Criteria

Donor hearts will be excluded if they meet any of the following criteria:

- CAD with $>50\%$ stenosis on angiogram, or
- Cardiogenic shock or myocardial infarction, or
- EF consistently $<40\%$, or
- Significant valve disease except for competent bicuspid aortic valve.

6.2. Recipient Eligibility Criteria

Recipient Inclusion Criteria

Recipients are required to meet all the following criteria on the day of transplant:

- Registered primary heart transplant candidate
- Age ≥ 18 years old
- Written informed consent.

Recipient Exclusion Criteria

Recipients will be excluded if they meet any of the following criteria on the day of transplant:

- Prior solid organ or bone marrow transplant
- Chronic use of hemodialysis or renal replacement therapy for diagnosis of chronic renal insufficiency requiring dialysis
- Multi-organ transplant.

6.3. Subject Enrollment and Screen Failures

As part of the screening process, the following must occur:

- Subject must be matched with a donor heart that meets eligibility criteria for Heart EXPAND CAP; and
- Subject must meet eligibility criteria for Heart EXPAND CAP; and
- The matched donor heart must be accepted for transplantation in the donor chest by the transplant surgeon or designee; and
- The matched donor heart must be instrumented on the OCS.

A subject will be considered a screen failure under the following conditions:

- The donor heart matched to this recipient fails to meet transplantability criteria per [Section 7.4](#) of the protocol following OCS Heart System instrumentation (i.e., donor heart turndown).
- The recipient fails to meet inclusion/exclusion criteria on the day of the potential transplant after an eligible donor heart is instrumented on the OCS™ Heart System and accepted for transplantation following OCS instrumentation preservation.
- Logistical reasons prevent transplantation of donor heart instrumented on the OCS™ Heart System that meets acceptance criteria for transplant following OCS preservation (e.g., transplant center or OPO issues, transportation or allocation issues, surgeons or ORs are unavailable).

A subject will be considered enrolled when the subject is transplanted with the OCS-instrumented organ.

Subjects who are screen failures that remain eligible for the study will return to the waiting list for another heart transplant. Depending on the donor match, this next transplant may be either in the Heart EXPAND CAP or the subject may be transplanted using standard cold storage and will not be enrolled in this study.

Medicare beneficiaries with a clinical need for transplantation will be treated in the same manner as patients not covered by a Medicare plan. The rules of participation and results of the study apply to Medicare and non-Medicare covered patients in the same manner.

7. PRE-OPERATIVE TRIAL PROCEDURES

7.1. Subject Identification

All patients on the transplant waiting list, or in the process of listing on the transplant waiting list, who are approached by trial investigators for consent for this trial will be identified in a “screening log.”

Those patients who initially appear eligible for the trial will have the trial explained to them, be invited to participate, and will be asked to sign an informed consent for participation in the trial prior to treatment. When a matching eligible donor heart becomes available, the inclusion and exclusion criteria for the recipient will be re-verified.

7.2. Recipient Day of Transplant Assessment

The purpose is to conduct a final assessment of whether the potential recipient still meets the eligibility criteria. The following information will be verified on the day of transplant:

- **Eligibility:** Investigator will review and confirm that the potential recipient is still a candidate for heart transplantation and continues to meet all inclusion criteria and no exclusion criteria for this study.
- **Demographics/Characteristics**
- **Recipient Risk Factors & Medical History**

7.3. Donor Screening and Acceptance

The investigator or a member of her/his transplant team will evaluate the donor and the quality and suitability of the heart for: (1) transplantation, according to his or her standard practice and (2) eligibility for the Heart EXPAND CAP. The following evaluations will be conducted:

- **Organ Donor Identification Number and Type of Registry (e.g., UNOS ID)**
- **Donor Demographics**
- **Donor Characteristics**
- **Donor's Cause of Death**
- **Donor Medical History**
- **Donor Social History**
- **Donor Heart Assessment:** An EF is required to determine subject eligibility. The donor heart can be assessed prior to procurement and acceptance using one or more of the following methods:
 - Angiogram findings (if available)
 - Echocardiogram findings (if available)
 - Final inspection and palpation prior to acceptance in the chest
- **Donor Eligibility:** The donor will be evaluated to document whether the eligibility criteria for Heart EXPAND CAP are met.

7.4. Donor Heart Retrieval and OCS Preservation and Assessment

After final evaluation of the donor heart in the donor's chest and after a decision is made to procure the organ for transplantation, donor eligibility for Heart EXPAND CAP will be reviewed. Upon acceptance into the trial, the investigators will retrieve and preserve the donor heart according to the OCS Heart Instructions for use (IFU).

7.4.1. Donor Heart Acceptance for Transplantation after OCS Preservation

Donor hearts preserved on the OCS should have stable parameters throughout perfusion after initial stabilization period (defined as the time period during which perfusion is initiated and primary parameter adjustments are made). Parameters should be maintained within the following ranges for acceptance:

- Final arterial perfusate lactate < 5 mmol/L with stable lactate trend
- Stability of OCS Heart Perfusion parameter trends over time within the guidance ranges below:
 - Aortic Pressure (mean AOP): 40-100 mmHg
 - Coronary Flow (CF): 400-900 mL/min.

Note: certain expanded criteria donor hearts may require perfusion with parameters outside of these guidance ranges. Acceptance for transplantation should be primarily based on an acceptable lactate trend/value.

7.4.2. Reject for Transplantation

Donor hearts preserved on the OCS will be rejected for any of the following:

- Transplanting surgeon and/or designee is clinically unsatisfied with donor heart condition/performance on the OCS Heart System at final evaluation, e.g., unstable and rising arterial lactate despite multiple maneuvers to optimize perfusion parameters (increasing AOP and/or CF)
- Final arterial perfusate lactate ≥ 5 mmol/L.

Any decision to turndown hearts after preservation and assessment on OCS™ Heart System should be documented on the appropriate CRF. Samples should be sent to the central core lab for assessment of any inherent cardiac pathology that was not diagnosed at retrieval of the donor heart.

8. TRANSPLANT, IMMEDIATE POST-OPERATIVE AND LONG TERM FOLLOW-UP

8.1. Transplant Details

The following information concerning the transplant procedure will be collected:

- The organ recipient unique post-transplant patient identifier
- Total cross clamp duration in minutes (from donor cross-clamp application to removal of cross-clamp in the recipient)
- Pre-OCS cold ischemia time (time from donor cross clamp until start of perfusion on OCS)
- Post-OCS cold ischemia time (time from heart flush on OCS until aortic cross-clamp removal in the recipient)
- Any surgical complications encountered during surgery.

8.2. Post Transplant Functional Assessments Day 0 – Day 30:

- Heart Primary Graft Dysfunction (PGD) Surveillance in the first 24 hours (see [Appendix 1](#))
- Initial use of Mechanical Circulatory Support
- Inotropic Support for first 24 hours: the following inotropic medication doses, if available, will be collected at ICU admission T0 and T24 hours after ICU admission post-heart transplantation:
 - Dopamine – mcg/kg/min
 - Dobutamine – mcg/kg/min
 - Amiodarone – mcg/kg/min
 - Milrinone – mcg/kg/min

- Epinephrine – mcg/kg/min
- Norepinephrine – mcg/kg/min
- Echocardiogram results in the first 24 hours
- Right Heart Catheter Data between ICU admission T0 and T24 hours after ICU admission post-heart transplantation (not required; collected only if performed as part of the institution's standard of care):
 - Pulmonary Artery Pressures (PAP)
 - Pulmonary Capillary Wedge Pressure (PCWP)
 - Cardiac index (CI)
 - Right Atrial Pressure (RAP)
 - Initial Post-Transplant ICU Stay
- Initial use of Mechanical Respiratory Support
- Initial Post-Transplant Hospital Stay
- Immunosuppression Medications
- Trans-thoracic echocardiogram prior to Discharge
- Patient and Graft Survival at Day 30 (+5 days), patient and graft survival will be assessed.
- Serious Adverse Events: All SAEs will be collected for the first 30 days post-transplant. SAEs will be followed until the investigator designates the event to be either resolved or its effect on the patient's condition stabilized.

8.3. Long Term Follow-up: 6 and 12 months:

Follow-up data collection will be conducted at 6 and 12 months post transplant. Although the follow-up may be done via phone contact; medical records may be needed for additional information.

- **6-Month Follow-Up:** At 6 months post transplant (\pm 30 days), the patient will be evaluated for:
 - Patient and graft survival
 - Whether the patient was re-hospitalized after initial discharge, and, if so, the primary reason for the hospitalization and the length of stay
 - Information will also be collected on any diagnosis of cardiac dysfunction and, if so, the method of diagnosis and treatment.
- **12-Month Follow-Up:** At 12 months (\pm 30 days) post transplant, the patient will be evaluated for:
 - Patient and graft survival
 - Any diagnosis of cardiac allograft vasculopathy and, if so, the method of diagnosis (e.g., IVUS, coronary angio).

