9.5. Reporting of Adverse Events

All SAE information will only be collected from transplant through day 30. Unanticipated adverse device effects (UADE) should be reported to TransMedics, Inc., within 48 hours of the time the investigator learns of the event, but in no case later than 5 working days after learning of the event.

SAEs should be entered into the study database as soon as possible. SAE will be followed until the investigator designates the event to be either resolved or its effect on the patient's condition stabilized. Details related to treatment of the SAE will also be collected.

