10.4. Safety

Safety will be analyzed principally by examination of the frequency of adverse events. In particular, the number of heart graft-related serious adverse events (HGRSAEs) up to the 30-day follow-up after transplantation per subject will be analyzed. This endpoint is defined to consist of the following adverse events (at most one per type), if they are serious adverse events:

- Moderate or severe primary heart graft dysfunction (PGD) (left or right ventricle) (not including rejection or cardiac tamponade) according to ISHLT consensus manuscript.
- Primary graft failure requiring re-transplantation.

This endpoint will be summarized using descriptive statistics, specifically the mean, median, standard deviation, minimum, maximum, and a 95% confidence interval for the mean based on the t-distribution.

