	Moderate PGD-LV: Must meet one criterion from I and another criterion from II:	I. One criteria from the following: Left ventricular ejection fraction \leq 40%, or Hemodynamic compromise with RAP $>$ 15 mm Hg, PCWP $>$ 20 mm Hg, CI $<$ 2.0 L/min/m ² , hypotension with MAP $<$ 70 mm Hg (lasting more than 1 hour) II. One criteria from the following: i. High-dose inotropes—Inotrope score $>$ 10 ^a or ii. Newly placed IABP (regardless of inotropes)
	Severe PGD-LV	Dependence on left or biventricular mechanical support including ECMO, LVAD, BiVAD, or percutaneous LVAD. Excludes requirement for IABP.
2. PGD-right ventricle (PGD-RV):	Diagnosis requires either both i and ii, or iii alone:	i. Hemodynamics with RAP $>$ 15 mm Hg, PCWP $<$ 15 mm Hg, CI $<$ 2.0 L/min/m ² ii. TPG $<$ 15 mm Hg and/or pulmonary artery systolic pressure $<$ 50 mm Hg, or iii. Need for RVAD

BiVAD, biventricular assist device; CI, cardiac index; ECMO, extracorporeal membrane oxygenation; IABP, intra-aortic balloon pump; LVAD, left ventricular assist device; PCWP, pulmonary capillary wedge pressure; RAP, right atrial pressure; RVAD, right ventricular assist device; TPG, transpulmonary pressure gradient.

^aInotrope score = dopamine (\times 1) + dobutamine (\times 1) + amrinone (\times 1) + milrinone (\times 15) + epinephrine (\times 100) + norepinephrine (\times 100)⁶⁷ with each drug dosed in μ g/kg/min.

Note: All incidences of PGD will be adjudicated by the Medical Monitor.

Hemodynamic data will be used in the assessment of PGD severity only if collected by centers as clinically indicated, per the institution's standard of care. This approach is consistent with contemporary U.S. publications on PGD using ISHLT criteria (Nicoara, 2018; Squiers, 2018). If hemodynamic data are not collected, the Medical Monitor will use available clinical data to adjudicate PGD severity grading.

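### The Section 8.2 inotrope dose list has amiodarone where the Appendix 1 inotrope score has amrinone, so one of six score inputs is not on the list.

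*Combined protocol and SAP*

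**What the plan says.** Under inotropic support, Section 8.2 states that "the following inotropic medication doses, if available, will be collected at ICU admission T0 and T24 hours" after ICU admission. It then names dopamine, dobutamine, amiodarone, milrinone, epinephrine and norepinephrine, each in mcg/kg/min. The third line reads "Amiodarone – mcg/kg/min".

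Footnote a of the Appendix 1 table defines the inotrope score as a weighted sum of dopamine (weight 1), dobutamine (1), amrinone (1), milrinone (15), epinephrine (100) and norepinephrine (100), in the same dose unit. For moderate PGD-LV a recipient "Must meet one criterion from I and another criterion from II". Group II is met by a score above 10 or by a newly placed IABP.

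Moderate PGD feeds the HGRSAE endpoint of Sections 5.3 and 10.4. Section 10.4 counts events with the qualifier "at most one per type), if they are serious adverse events".

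On adjudication, Appendix 1 says that "All incidences of PGD will be adjudicated by the Medical Monitor" and adds: "If hemodynamic data are not collected, the Medical Monitor will use available clinical data to adjudicate PGD severity grading".

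**The concern.** The list and the score have the same length, order and unit and differ only in the third entry. That looks like a transcription slip, although the documents do not say so. A site that follows Section 8.2 to the letter records a drug with no term in the score and has no line for one that has a term.

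The two possible errors run in opposite directions. An amrinone dose that is not recorded can only lower a score built from the listed fields, so a moderate PGD-LV could be missed. An amiodarone dose put into the vacant term can only raise it. Either would change the count in the HGRSAE endpoint, which is the plan's main safety summary.

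**Working it through.** **Step 1: compare the lists.**

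| Position | Section 8.2 list | Appendix 1 score (weight) | Match |
|---|---|---|---|
| 1 | dopamine | dopamine (1) | yes |
| 2 | dobutamine | dobutamine (1) | yes |
| 3 | amiodarone | amrinone (1) | no |
| 4 | milrinone | milrinone (15) | yes |
| 5 | epinephrine | epinephrine (100) | yes |
| 6 | norepinephrine | norepinephrine (100) | yes |

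Five of six match. Amrinone is only in the score and amiodarone only in the list. The Appendix 2 schedule has an Inotropic Support row at T0 and T24 but names no drugs, so it does not settle the difference.

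**Step 2: when could a grade change?** Let S be the sum of the five weighted terms that are collected and a the uncollected amrinone dose (weight 1). The full score is S + a. Criterion II changes only if S ≤ 10 < S + a and no new IABP is placed, and the grade changes only if criterion I is also met. The documents give no amrinone doses. For assumed values of a = 1, 2 and 5, S must lie above 9, 8 and 5 respectively and be no more than 10.

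**Step 3: what would one regrading do to the endpoint?** The plan states no figure to reproduce. As an illustration I use the Heart EXPAND counts in Section 2.2.7: 9 of 75 with moderate or severe PGD within 30 days and 1 re-transplantation, all assumed serious. With K events in n = 75 subjects and x the count per subject:

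- mean = K/75
- variance s² = (Σx² − K²/75)/74
- 95% half-width = t(0.975; 74 df) × s/√75, with t = 1.993

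The re-transplantation may be in a separate recipient (Σx² = K) or in one of the PGD recipients (one subject with x = 2, so Σx² = K + 2).

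For K = 10 with separate recipients, s² = (10 − 100/75)/74 = 0.1171, s = 0.342 and the half-width is 0.0787. For K = 10 in the same recipient, s² = (12 − 100/75)/74 = 0.1441, s = 0.380 and the half-width is 0.0874.

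| Events K | Mean | 95% CI, separate recipients | 95% CI, same recipient |
|---|---|---|---|
| 9 (one moderate PGD lost) | 0.120 | 0.045 to 0.195 | 0.036 to 0.204 |
| 10 | 0.133 | 0.055 to 0.212 | 0.046 to 0.221 |
| 11 (one added) | 0.147 | 0.065 to 0.229 | 0.056 to 0.237 |

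One regraded recipient shifts the mean by 1/75 = 0.0133. Against the half-width at 10 events this is 0.0133/0.0787 = 16.9% or 0.0133/0.0874 = 15.3%.

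**Step 4: how many events could depend on the score?** Section 2.2.7 also gives 8 of 75 with severe PGD in the first 24 hours. If those eight are among the nine, 9 − 8 = 1 recipient falls outside that severe group. The severe PGD-LV definition rests on mechanical support, and the PGD-RV definition does not use the score. On EXPAND counts, at most one event could then turn on the score.

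**The case against.** The strongest reply is that the list is not declared to be the input to the score. The bullet on "Heart Primary Graft Dysfunction (PGD) Surveillance in the first 24 hours" is separate and points straight to Appendix 1, where the score is given with its amrinone term. Appendix 2 has its own PGD Scores row at T24. All six doses are collected only where available, so an amrinone line would not guarantee a value either. The Medical Monitor adjudicates every PGD (Section 15.7 and Appendix 1) and is nowhere confined to the Section 8.2 fields. Section 9.5 adds that "Details related to treatment of the SAE will also be collected", and Section 14.4 provides for source document review. Scoring amiodarone would breach Appendix 1 rather than follow it.

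Much of this stands, and it limits the consequence. It does not remove the mismatch:

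- The availability wording excuses a missing value for a listed drug; it does not add an unlisted one.
- The written fallback to other clinical data is stated only for missing hemodynamic measurements.
- SAE treatment details are collected once an event has been recorded as an SAE, whereas the score helps decide whether a moderate PGD exists.
- None of these routes assures an amrinone dose in mcg/kg/min.

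The upward error does require someone to depart from Appendix 1, so it is the weaker of the two scenarios.

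**Conclusion.** The inconsistency is real and evident from the text: Section 8.2 supplies five of the six score inputs plus one drug that has no term. Confidence in the mismatch is high. Confidence in any effect on results is low, because the documents do not show how many recipients would receive amrinone or have amiodarone scored in error.

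It is minor. Severe PGD-LV and PGD-RV do not use the score, so the primary endpoint and the severe PGD endpoint are unaffected. The stopping rule counts deaths only. The HGRSAE analysis is descriptive, with no success threshold. The shift of 0.013 per regraded recipient rests on n = 75, and the intervals rest on the EXPAND counts with all events assumed serious. The reading that at most one EXPAND event could depend on the score also assumes that the eight severe cases are among the nine.

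**What to change.** Reconcile Section 8.2 with footnote a of Appendix 1 so that the drugs collected are those in the score. If amiodarone is still to be recorded for another purpose, state that it does not enter the score. Check the matching eCRF field. Appendix 4 shows no forms in this copy, so whether the form repeats the mismatch is unknown.

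The cost is one line of protocol text and one field check. No analysis or sample size changes.
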